Study Visits	
 ● Screening / Baseline Period (Day -21 to Day 0) 
Only after the subject signs the ICF approved by the Institutional Review Board (IRB), the screening and tumor assessment related to the clinical study can be initiated. During the screening period, the following tests will be performed: complete medical history, physical examination, height, weight, vital signs (blood pressure and heart rate), electrocardiogram (ECG), ECOG score, etc. Past medications and clinical laboratory tests, including urinalysis, hematology (differential blood count), blood chemistry, coagulation function, stool routine, myocardial zymogram, and lymphocyte subsets must be performed within one week before drug administration. Thyroid function, pituitary-adrenal axis function, virological parameters, and pregnancy test (only for women of childbearing potential) must be completed within 21 days before the first drug administration. Tumor assessment must be completed within 3 weeks before the administration of the study drug (additional nasopharyngeal MRI or CT for nasopharyngeal melanoma, additional oropharyngeal MRI or CT for oropharyngeal melanoma, colposcopy for female genital tract

--------------	--

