5.3. Dose modifications

During the study period, dose modifications of the investigational drug can be made based on its toxic side effects, including: dose interruption, dose reduction, modification of administration mode, and dose termination.

Dose interruption is allowed for SHR-1210, with a maximum allowable drug interruption of 12 weeks.

In addition to dose interruption, for subjects whose weight decreases to below 50 kg during the treatment period, the dose of SHR-1210 may be down-titrated to 3 mg/kg q2w, as appropriate.

Dose modifications due to apatinib-related toxicity include: dose interruption, dose reduction, modification of administration mode (first modification: 5 days on treatment and 2 days off; second modification: 7 days on treatment and 7 days off), and dose termination. During the study, after adjusting the administration mode of apatinib, the recovery of dose mode will not be allowed.

During the study, if definite apatinib-related AEs occur, such as hypertension, proteinuria, hand and foot syndrome (HFS), apatinib administration may be down-titrated or interrupted. After toxicity recovery, the original dose, adjusting the administration method, or terminating the dose may be given as appropriate. After discontinuing apatinib, the study subjects may continue to receive SHR-1210 monotherapy.

During the study, if immune-related toxicities occur, such as immune pneumonia,

hepatitis, enteritis, the administration of SHR-1210 and apatinib should be suspended as appropriate. Once the toxicity has recovered to \leq grade 1 or baseline levels (for the increase of laboratory parameters such as ALT/AST and total bilirubin [TBIL]), the medication can be resumed. The administration of SHR-1210 should be resumed first, and after 14 days of observation without significant abnormalities, the administration of apatinib can be initiated and the mode of subsequent administration of apatinib will be adjusted.

During the study, if \geq grade 3 immune pneumonia, \geq grade 3 TBIL increased, grade 4 ALT/AST increased, or other grade 4 immune-related toxic reactions, grade 4 injection reactions occur, or if the immune-related toxicity causes a temporary suspension of SHR-1210 administration for more than 12 weeks and still cannot recover to \leq grade 1 or baseline level, SHR-1210 must be permanently discontinued.

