During the study, if \geq grade 3 capillary hyperplasia occurs, no dose modifications are required for apatinib, and SHR-1210 should be suspended until the toxicity recovers to \leq grade 2.

During the study, if the subject exhibits abnormal symptoms/signs or laboratory indicators, symptomatic treatment should be taken promptly, and it is recommended to refer to the following table for corresponding dose modifications:

Table 1 Dose Modifications

Drug-related Toxicity		Grading	Dose Interrupted or Not		Criteria for Resumption of Dosing	Dose Modification Methods for Apatinib	Discontinuation Criteria
			SHR-1210	Apatinib			
SHR-1210 and apatinib-related toxicities	Hematologic toxicity	Grade 1 and 2	No	No	-	-	-
		Grade 3	Yes	Yes	When toxicity recovers to \leq grade 2	Original dose	After two modifications, if \geq grade 3 hematologic toxicity occurs again, the administration of apatinib will be terminated.
	Grade 4	Yes	Yes	When toxicity recovers to \leq grade 2	First modification: Adjust to 5 days on treatment and 2 days off; Second modification: Adjust to 7 days on treatment and 7 days off;		
	Immune-related	Grade 2	Yes	No	When toxicity recovers	First modification: Resume	Unable to recover to \leq grade

Drug-related Toxicity	Grading	Dose Interrupted or Not		Criteria for Resumption of Dosing	Dose Modification Methods for Apatinib	Discontinuation Criteria
		SHR-1210	Apatinib			
ated pneumonia				to ≤ grade 1	at original dose Second modification: Adjust to 5 days on treatment and 2 days off; Third modification: Adjust to 7 days on treatment and 7 days off	1 after > 12 weeks of discontinuation
ALT/AST and TBIL increased (after receiving	Grade 2 ALT or AST increased Grade 2 bilirubin	Yes	Yes	When toxicity returns to baseline	First modification: Adjust to 5 days on treatment and 2 days off; Second modification: Adjust to 7 days of on treatment	1. If discontinuation of the drug for >12 weeks still does not result in recovery to baseline levels, then terminate the use of

Drug-related Toxicity	Grading	Dose Interrupted or Not		Criteria for Resumption of Dosing	Dose Modification Methods for Apatinib	Discontinuation Criteria
		SHR-1210	Apatinib			
hepatoprotective treatment)	increased				and 7 days off;	SHR-1210.

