	Grade 3 ALT / AST increased	Yes	Yes	When toxicity returns to baseline	First modification: Adjust to 7 days on treatment and 7 days off; Second modification: Permanently discontinue apatinib	1. If discontinuation of the drug for >12 weeks still does not result in recovery to baseline levels, then terminate the use of SHR-1210. 2. If grade 3 ALT/AST increased occurs again, then terminate the use of

Drug-related Toxicity	Grading	Dose Interrupted or Not		Criteria for Resumption of Dosing	Dose Modification Methods for Apatinib	Discontinuation Criteria
		SHR-1210	Apatinib			
						SHR-1210.
Other nonhematologic toxicities	Grade 1	No	No	-	-	-
	Grade 2 (lasting for \geq 7 days)	Yes	Yes	When toxicity recovers to \leq grade 1	Original dose	Unable to recover to \leq grade 1 after > 12 weeks of discontinuation
	Grade 3	Yes	Yes	When toxicity recovers to \leq grade 1	First modification: Adjust to 5 days on treatment and 2 days off; Second modification: Adjust to 7 days on treatment and 7 days off;	
SHR-1210 Capillary	Grade 3	Yes	No	When toxicity recovers	Original dose	> 12 weeks of SHR-1210

Drug-related Toxicity		Grading	Dose Interrupted or Not		Criteria for Resumption of Dosing	Dose Modification Methods for Apatinib	Discontinuation Criteria
			SHR-1210	Apatinib			
-related toxicities	hemangioma				to ≤ grade 2		discontinuation
Apatinib-related toxicities	Hypertension	Grade 3 (After corrective treatment)	No	Yes	When toxicity recovers to ≤ grade 1	
First modification: Resume at original dose
 
Recurrent grade 3 hypertension: Adjust to 5 days on treatment and 2 days off for apatinib.
 
The third occurrence of grade 3 hypertension: Adjust to 7 days on treatment and 7 days off for apatinib.
	After two modifications, grade 3 hypertension occurs again, and the administration of apatinib will be terminated.

Drug-related Toxicity	Grading	Dose Interrupted or Not		Criteria for Resumption of Dosing	Dose Modification Methods for Apatinib	Discontinuation Criteria
		SHR-1210	Apatinib			
	Hypertensive crisis	Yes	Yes	When toxicity recovers to \leq grade 1	Permanently discontinue apatinib	Discontinue apatinib

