[Stool Routine] If fecal occult blood is positive, a re-examination is required. If fecal occult blood remains positive after re-examination, a gastroscopy is required;

[Blood Chemistry] ALT, AST, AKP, γ -GT, LDH, creatinine, potassium, sodium, blood lipase (only performed during the screening period and when abdominal pain, bloating, or other suspected pancreatitis symptoms occur), blood amylase (only performed during the screening period and when abdominal pain, bloating, or other suspected pancreatitis symptoms occur);

[Coagulation Function] includes INR, APTT, PT, and FIB;

[Myocardial Zymogram Examination] includes CK, CK-MB, α -hydroxybutyrate dehydrogenase, LDH, AST;

[Lymphocyte Subsets] include T cell subsets (CD3+, CD4+, CD8+), natural killer cells (CD16/56+), immunoglobulins (IgG, IgA, IgM); complement (C3) (to be performed within 14 days prior to treatment);

[Vital Signs] temperature, pulse, respiratory rate, blood pressure;

[Blood Pressure Monitoring] During the screening period, the investigator or study

nurse will measure blood pressure for patients. For each blood pressure measurement, smoking and coffee consumption are prohibited within 30 minutes prior to the measurement, and the patient should rest quietly for at least 10 minutes. The measurement should be taken in a seated position, with the elbow at the same level as the heart, and blood pressure should be measured on the same side each time.

[Physical Examination] General condition, head and face, skin, lymph nodes, eyes (sclera, pupils), ears, nose, throat, oral cavity, respiratory system, cardiovascular system, abdomen (including liver and spleen), reproductive-urinary system, musculoskeletal system, nervous system, and mental status; Note: A comprehensive physical examination must be conducted during the study period, and only abnormal findings need to be recorded in the CRF. If there is no change compared with the screening period, there is no need to repeat the recording.

[ECOG Score]

[12-Lead Electrocardiogram] If any abnormalities are identified, two additional confirmations must be performed, or other necessary examinations should be conducted based on the investigator's judgment.

[Echocardiography]

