6.2. Study Period

Cycle 1 Day 1: [Vital Signs] [Physical Examination and Body Weight Measurement]
[SHR-1210 Intravenous Infusion] [Apatinib Administration]

Within 24 hours after the first administration of SHR-1210, acute allergic reactions

should be closely monitored. If any occur, treatment should be carried out in accordance with the medical practices and relevant guidelines of this institution.

To improve patient compliance, on Day 1 of the first cycle, only SHR-1210 administration can be performed, and oral apatinib can be initiated on Day 2. The dose of apatinib can be adjusted according to the patient's tolerance, and it should be taken continuously, with 4 weeks for one cycle.

Cycle 1 Day 15: [Hematology] [Blood Chemistry] [Urinalysis] [Stool Routine] [Coagulation Function] [Vital Signs] [Physical Examination and Body Weight Measurement] [Electrocardiogram] [SHR-1210 Intravenous Infusion] [Adverse Events] [Concomitant Medications]

Day 1 in Subsequent Cycles: - [Hematology] [Blood Chemistry] [Urinalysis] [Stool Routine] – [Coagulation Function] [Vital Signs] [Physical Examination and Body Weight Measurement] [ECOG Score] [Electrocardiogram] [SHR-1210 Intravenous Infusion] [Adverse Events] [Concomitant Medications] [Recovery/Dispensing of Apatinib]

Day 15 in Subsequent Cycles: [Hematology] [Blood Chemistry] [Urinalysis] [Vital Signs] [Physical Examination and Body Weight Measurement] [SHR-1210 Intravenous Infusion] [Adverse Events] [Concomitant Medications]

A ± 3 -day window period will be set, and the intravenous infusion of SHR-1210 should be performed after completing the assessments of examinations and tests specified in the flowchart.

[Imaging Assessment] During the treatment period, imaging examinations should be conducted under the same conditions as the baseline examination (scan thickness, use of contrast agents, etc.). The lesions identified at baseline should be examined every 2 cycles during the first 12 treatment cycles (bone scans should be performed when

bone progression is suspected or CR confirmation is needed), and every 3 cycles thereafter. If new lesions are suspected, timely examinations can be performed. The first partial response (PR)/CR must be confirmed 4 weeks \pm 7 days later. If disease progression is observed for the first time according to RECIST v1.1, radiological examination should be performed 4 ~ 6 weeks later for confirmation (except for rapid progression and significant clinical progression).

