6.3. End of treatment / withdrawal

If a patient experiences an event that meets the criteria in "4.3.1 Discontinuation Criteria", the patient's treatment will be terminated. At the end of the study treatment or withdrawal from the study, if the patient has not been examined within 14 days prior to the end of the study, the following tests should be conducted:

[Hematology] [Blood Chemistry] [Urinalysis] [Stool Routine] [Coagulation Function]
[Pregnancy Test] [Thyroid Function Test] [Myocardial Zymogram] [Vital Signs]

[Physical Examination] [ECOG Score] [Electrocardiogram] [Blood Pressure Monitoring] [Adverse Events] [Concomitant Medications] [Recovery of Apatinib]

If no imaging examination has been performed within 4 weeks prior to the end of treatment, an imaging examination should be conducted at the end of the study treatment or upon withdrawal from the study for efficacy evaluation. For patients with non-imaging evidence of progression (intolerable, other circumstances), tumor assessments should be performed every 3 months until disease progression, death, or initiation of other anti-tumor treatments.

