6.4. Follow-up

Thirty (30) days after the termination/completion of treatment (30 days \pm 3 days after the last administration of the investigational drug)

[Vital Signs] [Physical Examination] [ECOG Score] [Hematology] [Urinalysis] [Blood Chemistry] [Adverse Events] [Concomitant Medications]

SAEs and irAEs will be followed up within 90 days after the last administration of SHR-1210. If the patient initiates a new anti-tumor treatment, follow-up should be performed until the initiation of the anti-tumor treatment if it starts within 30 days after the last administration, follow-up should be performed until at least 30 days after the last administration; if it starts after 30 days, follow-up should be performed until the initiation of the anti-tumor treatment).

[Survival Follow-up] After the termination of the study treatment, the survival status and subsequent anti-tumor treatment information can be collected every month through clinical follow-up or telephone follow-up until death.

7. Evaluation

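### The only itemised blood chemistry panel (Protocol 6.1) omits total bilirubin, although Section 5.3 and Table 1 hold both drugs and permanently stop SHR-1210 on it

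*Protocol*

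**What the plan says.** **The panel.** Section 6.1 lists [Blood Chemistry] as ALT, AST, AKP, γ-GT, "LDH, creatinine, potassium, sodium, blood lipase (only performed during the screening period and when abdominal pain" or similar symptoms arise, and amylase under the same restriction. There is no catch-all wording, and no other panel in Section 6.1 contains bilirubin.

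**Where the label is reused.** The synopsis (Study Visits) names the panel without itemising it: "hematology (differential blood count), blood chemistry, coagulation function, stool routine". Section 6.2 uses the label at Cycle 1 Day 15, at Day 1 of later cycles and at Day 15 of later cycles. Section 6.3 uses it at end of treatment, and Section 6.4 at the 30-day visit. None of these gives a list of its own.

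**The rules that depend on bilirubin.**
- Table 1 holds SHR-1210 and apatinib together for the row "Grade 2 ALT or AST increased Grade 2 bilirubin" increase. Dosing resumes on return to baseline.
- The text of Section 5.3 requires permanent discontinuation of SHR-1210 for events at or above "grade 3 TBIL increased, grade 4 ALT/AST increased, or other grade 4 immune-related toxic reactions".
- For a grade 3 transaminase rise, Table 1 prescribes a hold first. The stop comes on recurrence: "If grade 3 ALT/AST increased occurs again, then terminate the use of" SHR-1210.

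**Eligibility.** Inclusion criterion 7 (Section 4.1) requires bilirubin at or below 1.5 × ULN within 7 days before the first dose.

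**The concern.** A dosing rule works only if the variable that triggers it is measured. The other laboratory and blood pressure triggers in Table 1 have a named input in Section 6: neutrophils, hemoglobin and platelets for hematologic toxicity, urine protein for proteinuria, blood pressure readings for hypertension, and ALT and AST for hepatic toxicity. Bilirubin is the exception, which looks like an oversight.

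The point is first detection during treatment. Once a rise is known, Section 8.2.5 requires follow-up to resolution, baseline or stability, and Section 9.1 requires close monitoring of liver function in hepatitis. The resumption rule is therefore not in question. Before a rise is known, a site that orders exactly the printed panel would have no bilirubin value to grade.

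Two things are at stake. Patients could stay on a combination that the protocol says to hold or stop. The planned summary of worst laboratory grades (Section 10.5.4) would also have no scheduled post-baseline bilirubin behind it.

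**Working it through.** The plan states no figure on this point, so the check is a count and a comparison of texts.

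**1. Panel content (Section 6.1).** ALT, AST, AKP, γ-GT, LDH, creatinine, potassium, sodium, lipase, amylase.
- Analytes listed: 10.
- Restricted to screening or suspected pancreatitis: 2 (lipase, amylase).
- Applying routinely on treatment: 10 − 2 = 8.
- Bilirubin among them: 0.

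The restriction on lipase and amylase matters for reading the list. It separates screening from later use, so the list was written to define the label after screening as well.

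**2. Reach of the label (Sections 6.2 to 6.4).** Three dosing visit types, plus end of treatment, plus the 30-day visit: 3 + 1 + 1 = 5 visit types. Redefinitions of the panel among them: 0. Other itemised chemistry lists in the protocol: 0.

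**3. Rules against measurements.**

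| Event | Action in Section 5.3 / Table 1 | In the 6.1 panel? |
|---|---|---|
| Grade 2 ALT or AST | Hold both drugs | Yes |
| Grade 2 bilirubin | Hold both drugs | No |
| First grade 3 ALT/AST | Hold both drugs | Yes |
| Second grade 3 ALT/AST | Stop SHR-1210 | Yes |
| Grade 4 ALT/AST | Permanently stop SHR-1210 | Yes |
| Grade 3 or higher bilirubin | Permanently stop SHR-1210 | No |

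**4. Can transaminases stand in?** Not for the decision. At a first grade 3 event, bilirubin calls for a permanent stop and ALT/AST for a hold. If both reached grade 3 and only the transaminases were measured, the patient would be handled under the more lenient rule. If bilirubin rose alone, no rule based on ALT or AST would be triggered.

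**5. Other routes to a bilirubin value.**
- *Inclusion criterion 7:* forces a value before the first dose only.
- *Section 5.1.5:* requires all necessary examinations within 72 hours before each SHR-1210 dose, but names no analyte.
- *Section 9.1, hepatitis:* gives liver discomfort and raised transaminases as examples of what to watch for, not bilirubin.
- *Physical examination (Sections 6.1 and 6.2):* covers skin, sclera and liver at dosing visits, so it relies on visible or palpable signs.
- *AKP and γ-GT:* in the panel, but tied to no named rule in Table 1.
- *Study Flow Chart (Section 6, opening, and Section 6.2):* governs testing, but is not in the text at hand.

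None of the routes that can be read names bilirubin as a scheduled on-treatment test.

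**The case against.** The strongest reply is that the governing schedule cannot be seen. Section 6 says tests follow the Study Flow Chart, and Section 6.2 makes each infusion wait for the tests in it. If the chart itemises bilirubin, patients are covered. This stands as a limit on how serious the gap is. It does not rescue Section 6.1: if the chart repeats the label, bilirubin is unscheduled, and if it itemises bilirubin, the printed list disagrees with it. Both cases need the same correction.

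A second reply is that the list cannot be exhaustive. Criterion 7 also requires serum albumin, which the panel omits as well, so sites must already test beyond it. On this view, an investigator who has to apply the bilirubin rules would treat bilirubin as a necessary examination under Section 5.1.5. That is a reasonable reading, and it makes a deliberate omission unlikely. It still leaves a mandatory stop resting on inference, when the chemistry list has no open-ended wording and sets limits analyte by analyte.

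A third reply is that stop thresholds say nothing about detection. A bilirubin rise accompanied by a grade 2 or higher transaminase rise would very probably be found, since both drugs are already held at that point and hepatitis brings closer liver monitoring. This is largely right for detection, and it narrows the exposure mainly to a rise without a qualifying ALT/AST rise. The contrast in thresholds still matters, because it shows that the correct action cannot be read off the transaminases alone.

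Finally, the primary endpoint (ORR) and its analysis are unaffected, and no impact has been quantified. Both statements are true.

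**Conclusion.** The point holds. The only itemised chemistry panel lists 10 analytes and no bilirubin, and it carries unchanged to 5 visit types. Section 5.3 and Table 1 nevertheless attach a hold of both drugs and a mandatory permanent stop of SHR-1210 to bilirubin. Section 6.1 is thus inconsistent with the protocol's own dosing rules, and with its 7-day eligibility requirement. This is more than detail that could be left to another document.

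The counts describe the gap, not its consequences. The protocol gives no rate of isolated bilirubin rise, so missed holds or stops cannot be estimated. The conclusion assumes that sites follow the printed panel and that the Study Flow Chart does not itemise bilirubin. If the chart does, what remains is a discrepancy between the chart and Section 6.1. Confidence is therefore medium. It should be fixed because it concerns patient safety, but it does not threaten the efficacy result.

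**What to change.** Add total bilirubin to the [Blood Chemistry] definition in Section 6.1, so that it is measured at screening and at every visit that uses the label, and make the Study Flow Chart agree. All thresholds and actions in Section 5.3 and Table 1 stay as they are.

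The change is one term in Section 6.1 and, if needed, one matching line in the flow chart. The running cost is one routine assay on a sample already being drawn, with no extra visit or blood draw.

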6.2. Study Period

Cycle 1 Day 1: [Vital Signs] [Physical Examination and Body Weight Measurement]
[SHR-1210 Intravenous Infusion] [Apatinib Administration]

Within 24 hours after the first administration of SHR-1210, acute allergic reactions

should be closely monitored. If any occur, treatment should be carried out in accordance with the medical practices and relevant guidelines of this institution.

To improve patient compliance, on Day 1 of the first cycle, only SHR-1210 administration can be performed, and oral apatinib can be initiated on Day 2. The dose of apatinib can be adjusted according to the patient's tolerance, and it should be taken continuously, with 4 weeks for one cycle.

Cycle 1 Day 15: [Hematology] [Blood Chemistry] [Urinalysis] [Stool Routine] [Coagulation Function] [Vital Signs] [Physical Examination and Body Weight Measurement] [Electrocardiogram] [SHR-1210 Intravenous Infusion] [Adverse Events] [Concomitant Medications]

Day 1 in Subsequent Cycles: - [Hematology] [Blood Chemistry] [Urinalysis] [Stool Routine] – [Coagulation Function] [Vital Signs] [Physical Examination and Body Weight Measurement] [ECOG Score] [Electrocardiogram] [SHR-1210 Intravenous Infusion] [Adverse Events] [Concomitant Medications] [Recovery/Dispensing of Apatinib]

Day 15 in Subsequent Cycles: [Hematology] [Blood Chemistry] [Urinalysis] [Vital Signs] [Physical Examination and Body Weight Measurement] [SHR-1210 Intravenous Infusion] [Adverse Events] [Concomitant Medications]

A ± 3 -day window period will be set, and the intravenous infusion of SHR-1210 should be performed after completing the assessments of examinations and tests specified in the flowchart.

[Imaging Assessment] During the treatment period, imaging examinations should be conducted under the same conditions as the baseline examination (scan thickness, use of contrast agents, etc.). The lesions identified at baseline should be examined every 2 cycles during the first 12 treatment cycles (bone scans should be performed when

bone progression is suspected or CR confirmation is needed), and every 3 cycles thereafter. If new lesions are suspected, timely examinations can be performed. The first partial response (PR)/CR must be confirmed 4 weeks \pm 7 days later. If disease progression is observed for the first time according to RECIST v1.1, radiological examination should be performed 4 ~ 6 weeks later for confirmation (except for rapid progression and significant clinical progression).

The allowable window period for imaging examination is \pm 7 days. Unscheduled imaging examinations can be performed when disease progression is suspected (e.g., worsening of symptoms).

[Thyroid Function Test] The test will be performed on Day 1 \pm 7 days of Cycle 2, and performed subsequently once on Day 1 \pm 7 days of each following cycle;

[Blood Pressure Monitoring] During the treatment period, blood pressure monitoring will be performed by the patients themselves and recorded in the patient's diary card. In the first two cycles, blood pressure should be measured at least three times per week. If blood pressure is abnormal, daily monitoring is required; if blood pressure is normal, blood pressure should be measured at least twice per week after the first two cycles. Additionally, at each follow-up visit, the investigator or study nurse will measure the patient's blood pressure.

